1.4 Summary of Clinical Experience

Nirsevimab has been investigated in 3 completed clinical studies (see the current Investigator's Brochure for additional detail on nirsevimab clinical development).

1.4.1 Phase 1a Study D5290C00001

Study D5290C00001 was a first-time-in-human Phase 1a, randomized, double-blind, placebo-controlled, dose-escalation study conducted to evaluate the safety, tolerability, PK, and ADA of nirsevimab compared to placebo in healthy adult volunteers (Griffin et al, 2017). This study was completed in June 2015. A total of 136 subjects were randomized and received a single fixed dose of nirsevimab (6 subjects each at doses of 300 mg IV, 1,000 mg IV, 3,000 mg IV, 100 mg IM, and 78 subjects at 300 mg IM) or placebo (34 subjects). All subjects were followed for approximately 360 days after dosing.

Safety

The safety profile of nirsevimab was favorable, with similar proportions of treatment-emergent adverse events (TEAEs) reported in the placebo (61.8%) group and the nirsevimab (62.7%) total group. Two treatment-emergent serious adverse events (TESAEs; gunshot wound and appendicitis) were reported in 2 nirsevimab subjects. TEAEs judged to be related to investigational product were reported in 29.4% of subjects in the placebo group, and 17.6% of subjects in the nirsevimab total group. The most frequent TEAEs in the nirsevimab total group included upper respiratory tract infection (URTI; 18.6%); headache (8.8%); urinary tract infection (5.9%); and dermatitis contact, musculoskeletal pain, nausea, and vomiting (4.9% each). The most frequently occurring TEAEs in the placebo group were headache (17.6%); URTI (8.8%); and nausea, increased blood creatine phosphokinase level, and paresthesia (5.9% each). There were no adverse events of special interest (AESIs) or new onset chronic diseases (NOCDs). There were no deaths. No safety signals in this healthy adult population were observed. These results demonstrated an acceptable safety profile for nirsevimab, including no observed hypersensitivity reactions, and supported further clinical studies of IM administration of 1 dose of nirsevimab in the target population of infants to provide protection for the duration of the RSV season.

Pharmacokinetics

A 2-compartment PK model adequately described the PK profile following both IV and IM administrations. Body weight was determined to be a significant covariate on systemic clearance and volume of distribution with allometric exponents. The mean population clearance and volume of distribution were 42.3 mL/day and 2.8 L, respectively. The mean $t_{1/2}$ of nirsevimab ranged from 85 to 117 days across dose groups, and bioavailability after IM administration was 77%. The predicted 3- to 4-fold increase in the $t_{1/2}$ of nirsevimab compared to a standard IgG antibody was confirmed.

Antidrug Antibody

Post-baseline ADA was detected in 13.7% of subjects in the nirsevimab total group and 15.2% of subjects in the placebo group, with a maximum titer of 1:800 and 1:400, respectively. On Day 361, ADA was detected in 5.3% of nirsevimab subjects and 10.7% of

placebo subjects. The highest titer at Day 361 was 1:200 for both the nirsevimab and placebo groups. The presence and titer of ADA had no effect on the PK or safety profiles.

The most frequently reported TEAEs for the nirsevimab group were URTI (69.0%), gastroenteritis (29.6%), cough (25.4%), pyrexia (22.5%), and otitis media (21.1%). There were no trends by dose of nirsevimab for these events. The most frequently reported TEAEs in the placebo group were URTI (66.7%), anemia (33.3%), and gastroenteritis, cough, and otitis media (22.2% each). Skin rashes (defined as adverse events [AEs] that coded to the Medical Dictionary for Regulatory Activities [MedDRA] preferred terms of dermatitis, dermatitis allergic, dermatitis atopic, dermatitis contact, dermatitis diaper, dry skin, eczema,

rash, and rash papular) were reported for 38.9% of subjects in the placebo group and 47.9% of subjects in the nirsevimab group. No skin events were consistent with hypersensitivity.

Pharmacokinetics

Nirsevimab exhibited a less-than-dose-proportional exposure increase between the 10- and 25-mg doses; however, exposure increase was dose proportional between 25- and 50-mg doses. Following a single IM dose of 10, 25, or 50 mg, the estimated $t_{1/2}$ of nirsevimab ranged from 62.5 to 72.9 days. On Day 151, 87% of the nirsevimab serum concentrations following the 50-mg IM dose were above the 90% effective concentration threshold of 6.8 μ g/mL.

Antidrug Antibody

ADA was not detected in any subject at Day 151. Post-baseline ADA was detected at Day 361 only in 18/68 (26.5%) subjects, and there were 2 subjects with transient ADA-positive titers at Day 50 only who were ADA negative at Day 361. Overall, post-baseline ADA was detected in 20/71 subjects (28.2%) in the nirsevimab group and 0/17 subjects (0%) in the placebo group. None of the post-baseline nirsevimab ADA-positive subjects were ADA positive at baseline; only one subject (in the placebo group) was ADA positive at baseline. The highest titer detected was 1:25,600 (observed in 2 subjects [2.8%]). The 20 subjects in the nirsevimab group who had ADA detected were positive for the presence of ADA targeting the YTE substitution and 4 of the 20 subjects with samples available had neutralizing ADA.

There was no impact of the presence of ADA on safety. ADAs did not appear to impact PK for 150 days after dosing. Serum anti-RSV neutralizing antibody titers increased dose-dependently following administration of nirsevimab and were higher than placebo by Day 8 and through Day 151. Serum nirsevimab concentrations were correlated with serum anti-RSV neutralizing antibody across all the dose levels, confirming anti-RSV activity of nirsevimab.

1.4.3 Phase 2b Study D5290C00003

Study D5290C00003 was a Phase 2b global, randomized, double-blind, placebo-controlled, single-dose study to evaluate the efficacy, safety, PK, and ADA of nirsevimab in healthy preterm infants, born between 29 weeks 0 days and 34 weeks 6 days GA, entering their first RSV season. Subjects were not eligible for RSV prophylaxis with palivizumab based on the Joint Committee on Vaccination and Immunisation, American Academy of Pediatrics, or other local or national guidelines, allowing for a placebo comparator group. Overall, 1,453 subjects were randomized 2:1 to receive a single dose of 50 mg IM nirsevimab or placebo. A total of 1,447 subjects were dosed, including 968 subjects in the nirsevimab group and 479 subjects in the placebo group. Subjects were followed for approximately 360 days after dosing.

Efficacy

Based on the analysis in the Intent-to-treat Population, a single dose of 50 mg IM nirsevimab resulted in a 70.1% (95% confidence interval [CI]: 52.3%, 81.2%; $p < 0.0001$) relative risk reduction (RRR) in the incidence of medically attended RSV-confirmed LRTI through Day 151 when compared to placebo. Additionally, a 78.4% (95% CI: 51.9%, 90.3%; $p = 0.0002$) RRR in the incidence of RSV LRTI hospitalization through Day 151 was seen in the nirsevimab recipients when compared to placebo.

Safety

The safety profile of nirsevimab was similar to that of placebo, with no new identified risks. Overall, 86.2% of subjects in the nirsevimab group and 86.8% of subjects in the placebo group had at least 1 TEAE. TEAEs \leq 1 day post dose occurred in 2.5% of subjects in both groups. In comparison to the placebo group, the nirsevimab group had a numerically lower incidence of TEAEs occurring \leq 7 days post dose (nirsevimab 12.5%, placebo 15.2%), TEAEs \geq Grade 3 in severity (nirsevimab 8.0%, placebo 12.5%), or TESAEs (nirsevimab 11.2%, placebo 16.9%). The majority of the TEAEs were mild or moderate in severity. The most common TESAEs, based on the nirsevimab group, were bronchiolitis (2.1% nirsevimab, 4.4% placebo), LRTI (1.4% nirsevimab, 2.7% placebo), bronchitis (1.4% nirsevimab, 2.3% placebo), and pneumonia (1.3% nirsevimab, 2.1% placebo). None of the TESAEs were considered related to investigational product by the Investigator. Five deaths were reported during the study through Day 361, including 2 subjects (0.2%) in the nirsevimab group and 3 subjects (0.6%) in the placebo group. None of the deaths were considered to be related to investigational product according to the Investigator.

Overall, the incidence of treatment-related TEAEs (nirsevimab 2.3%, placebo 2.1%); AESIs, including hypersensitivity, immune complex disease, and thrombocytopenia (nirsevimab 0.5%, placebo 0.6%); and NOCDs (nirsevimab 0.4%, placebo 0.8%) was low and generally comparable between the placebo and nirsevimab groups. AESIs were reported in 5 subjects (4 subjects with rash or rash macular and 1 subject with petechiae) in the nirsevimab group and 3 subjects (rash or rash papular) in the placebo group. All events were Grade 1 in severity. The TEAE of petechiae that was reported as an AESI was 1 day in duration and was reported by the Site Investigator based on description by the parent. There were no laboratory assessments for the petechiae.

TEAEs that involved the skin and subcutaneous tissues (including diaper rash) were collected as skin reactions, with a few exceptions for skin reactions that could be definitively diagnosed such as impetigo, varicella, and scabies. Skin reactions were reported in a similar percentage of subjects in both treatment groups (nirsevimab 32.9%, placebo 30.9%).

Pharmacokinetics

Following a single fixed 50-mg IM dose of nirsevimab, 97.8% of measurable Day 151 serum concentrations were above the nonclinical 90% effective concentration target of 6.8 μ g/mL. The mean (% coefficient of variation) area under the concentration-time curve from time 0 to infinity ($AUC_{0-\infty}$) and estimated apparent $t_{1/2}$ were 5,176.3 (35.0) day· μ g/mL and 59.3 (9.6) days, respectively.

Antidrug Antibody

Overall, the rate and titers of ADA were low, and in post-baseline ADA-positive subjects there was no apparent effect on PK or safety. Of the subjects who had serum samples available for testing, ADA was detected post baseline in 5.6% (52/929) of subjects in the nirsevimab group and 3.8% (18/469) of subjects in the placebo group. ADA titers ranged from 1:50 to 1:6,400 in the nirsevimab group and from 1:50 to 1:400 in the placebo group. Of the nirsevimab subjects who were post-baseline ADA positive, ADA targeting the YTE domain was observed in 4/17 subjects (23.5%) on Day 151 and 23/30 subjects (76.7%) on Day 361. Three nirsevimab subjects had NAb on Day 361.

1.5 Rationale for Conducting the Study

Prevention of RSV illnesses in all infants is a major public health priority; however, despite more than 50 years of attempted vaccine development, there are no licensed vaccines. While RSV prevention exists in the form of a specific RSV IgG (palivizumab) requiring 5 once-monthly injections, it is licensed only for infants who experience the greatest morbidity and mortality from RSV: preterm infants born \leq 35 weeks GA, children with CLD of prematurity, children with hemodynamically significant CHD and, in Japan, children \leq 24 months of age with immunocompromised conditions and Down syndrome. Nirsevimab is being developed as a cost-effective opportunity to protect all infants from RSV disease based on improved potency and an extended $t_{1/2}$, which is expected to support once-per-RSV-season dosing.

The nirsevimab clinical development program includes 2 pivotal studies for infants entering their first RSV season: the completed Phase 2b study (D5290C00003) and an ongoing Phase 3 study (D5290C00004) in healthy late term and term infants. Because of the significant advantage of one dose per RSV-season that nirsevimab would provide, the Sponsor recognizes the potentially important benefits for the pediatric population receiving palivizumab who must receive monthly injections during the RSV-season for protection. A Phase 2/3 study (D5290C0005) is currently being conducted in the high-risk palivizumab-eligible population entering their first and second RSV seasons. In addition, this Phase 2 study is planned to support an indication for a single dose of nirsevimab at the start of the RSV season in immunocompromised children who are \leq 24 months of age.

Primarily, the PK data in this study will be used to assess whether nirsevimab systemic exposure is altered in this population as compared to healthy infants. The effects of immune

status on exposure will be evaluated using population PK methods. Assuming similar exposure-response relationship, exposure matching principles will be used to support extrapolation of the observed clinical efficacy of nirsevimab from the Phase 2b, and Phase 3 studies in healthy infants.

1.6 Benefit-Risk and Ethical Assessment

The study will be performed in accordance with ethical principles that have their origin in the Declaration of Helsinki and are consistent with International Council for Harmonisation (ICH)/Good Clinical Practice (GCP), and applicable regulatory requirements.

To evaluate the clinical benefit-risk balance for nirsevimab, nonclinical and clinical data have been taken into consideration. Based on the risk of serious RSV disease in infants and high-risk children, there is an established unmet medical need for the use of nirsevimab for prophylaxis in all infants entering their first RSV season and in high-risk preterm infants and children \leq 24 months of age with CLD or CHD. Additionally, in Japan, palivizumab is approved for use in immunocompromised children \leq 24 months of age. Children in this study (ie, \leq 24 months of age with an immunocompromised medical condition) who receive nirsevimab may potentially benefit by being protected against serious RSV disease.

Nirsevimab is expected to provide similar efficacy benefits as palivizumab with the advantage of requiring a single IM dose instead of the 5 IM doses required for palivizumab.

Nirsevimab has no endogenous targets, and no safety concerns were identified in nonclinical studies. The potential risks are based primarily on safety risks that may be observed with any immunoglobulin, including mAbs such as palivizumab. These potential risks include, but are not limited to, hypersensitivity (including anaphylaxis), immune complex disease, thrombocytopenia, and injection site reactions. To date, there have been no observed events of anaphylaxis, significant hypersensitivity reactions, immune complex disease, or thrombocytopenia attributable to nirsevimab in the clinical studies. Nonetheless, subjects in nirsevimab clinical studies will continue to be monitored for important potential risks, and routine pharmacovigilance and risk minimization activities will be performed accordingly.

The benefit-risk assessment for nirsevimab in prevention of RSV disease based on the development through Phase 2b is favorable.

2 OBJECTIVES AND ENDPOINTS

2.1 Primary Objective and Associated Endpoint

The primary objective and associated endpoints are described in [Table 1](#).

Table 1 Primary Objective and Associated Endpoints

Type	Objective	Endpoint
Safety	To evaluate the safety and tolerability of nirsevimab when administered to immunocompromised children \leq 24 months of age	All TEAEs, TESAEs, AESIs, and NOCDs

AESI = adverse event of special interest; NOCD = new onset chronic disease; TEAE = treatment-emergent adverse event; TESAE = treatment-emergent serious adverse event.

2.2 Secondary Objectives and Associated Endpoints

The secondary objectives and associated endpoints are described in [Table 2](#).

Table 2 Secondary Objectives and Associated Endpoints

Type	Objective	Endpoint
PK	To evaluate the PK of nirsevimab	Summary of nirsevimab serum concentrations
ADA	To evaluate ADA responses to nirsevimab in serum	Incidence of ADA to nirsevimab in serum
Efficacy	To assess the efficacy of nirsevimab when administered as a single IM dose to infants \leq 24 months of age	Incidence of medically attended LRTI (inpatient and outpatient) and hospitalizations due to RT-PCR-confirmed RSV through 150 days after administration of nirsevimab

ADA = antidrug antibody; IM = intramuscular; LRTI = lower respiratory tract infection; PK = pharmacokinetics; RSV = respiratory syncytial virus; RT-PCR = reverse transcriptase-polymerase chain reaction.

2.3 Exploratory Objectives and Associated Endpoints

The exploratory objectives and associated endpoints are described in [Table 3](#).

Table 3 Exploratory Objectives and Associated Endpoints

Type	Objective	Endpoint
CCI		

Table 3 Exploratory Objectives and Associated Endpoints

Type	Objective	Endpoint
CC1		
HRU	To assess HRU for nirsevimab recipients	Magnitude of HRU (eg, number of admissions to hospitals and ICUs and duration of stay; number of subjects who require respiratory support and supplemental oxygen and duration of use; number and type of outpatient visits, eg, ER, urgent care, outpatient clinic; and number of prescription and OTC medications) for nirsevimab recipients

ER = emergency room; HRU = healthcare resource utilization; ICU = intensive care unit; OTC = over-the-counter; RSV = respiratory syncytial virus.

3 STUDY DESIGN

3.1 Description of the Study

3.1.1 Overview

Study D5290C00008 is a Phase 2, open-label, uncontrolled single-dose study to assess the safety and tolerability, PK, occurrence of ADA, and efficacy of nirsevimab in immunocompromised children who are \leq 24 months of age at the time of dose administration. The study is planned to be conducted in South Africa, the US, and the EU, in addition to Japan, where the study is currently ongoing. Approximately 100 subjects will be enrolled. Approximately 50 subjects entering their first RSV season will receive nirsevimab as a single, fixed IM dose of 50 mg if body weight $<$ 5 kg or 100 mg if body weight \geq 5 kg. Approximately 50 subjects entering their second RSV season will receive nirsevimab as a single, fixed IM dose of 200 mg. Subjects will be followed approximately 1 year after dose administration.

[figure not shown]
Subjects will be monitored throughout the study for LRTI. All subjects seeking medical attention for a respiratory illness (inpatient or outpatient setting) will be evaluated for the occurrence of LRTI. All subjects found to have a LRTI and all subjects who require hospitalization for a respiratory infection, even if there is not a diagnosis of LRTI, should have respiratory samples obtained and respiratory assessment forms completed. Samples should be collected for all of these respiratory events, even those not meeting the protocol-defined endpoint of LRTI. Subjects who have a primary hospitalization for a respiratory infection (ie, upper or lower respiratory tract), a respiratory deterioration during a hospitalization, or who seek outpatient medical attention (including emergency room [ER] visits) for a lower respiratory illness, will be assessed clinically for the presence of LRTI and for RSV by central laboratory diagnostic testing of respiratory secretions.

In addition to the clinical assessment of LRTI, there is a protocol definition using objective criteria for the determination of a protocol-defined medically attended LRTI. To meet the protocol-defined endpoint of medically attended LRTI, subjects with signs of LRTI must have documented at least one physical examination finding of rhonchi, rales, crackles, or wheeze AND at least 1 of the following clinical signs:

- Increased respiratory rate at rest (age < 2 months, \geq 60 breaths/min; age 2 to 6 months, \geq 50 breaths/min; age > 6 months, \geq 40 breaths/min), OR
- Hypoxemia (in room air: oxygen saturation < 95% at altitudes \leq 1,800 meters or < 92% at altitudes > 1,800 meters), OR
- Clinical signs of severe respiratory disease (eg, acute hypoxic or ventilatory failure, new onset apnea, nasal flaring, intercostal, subcostal or supraclavicular retractions, grunting) or dehydration secondary to inadequate oral intake due to respiratory distress (need for IV fluid).

Testing for RSV will be performed centrally using the US Food and Drug Administration (FDA)-cleared and Conformité Européenne or European Conformity-marked in vitro diagnostic real-time RT-PCR assay (Lyra RSV + hMPV Assay, Quidel, San Diego, CA; www.quidel.com). A diagnosis of RSV LRTI requires having a respiratory sample positive for RSV by the central laboratory RT-PCR.

Figure 1 Study Flow Diagram

IM = intramuscular; LRTI = lower respiratory tract infection; n = number of patients; RSV = respiratory syncytial virus.

The endpoints to be measured in this study are described in Section 2.

3.1.2 Treatment Regimen

As this is a single-arm study, all subjects will receive nirsevimab. Subjects who are in their first year of life AND entering their first RSV season at the time of dose administration will receive nirsevimab as a single, fixed IM dose of 50 mg if body weight < 5 kg or 100 mg if body weight ≥ 5 kg ($n = \sim 50$). Subjects in their second year of life AND entering their second RSV season at the time of dose administration will receive nirsevimab as a single, fixed IM dose of 200 mg ($n = \sim 50$).

3.2 Rationale for Dose, Population, and Endpoints

3.2.1 Dose Rationale

A single fixed 50-mg IM dose was shown to be efficacious in the Phase 2b Study D5290C00003 in preterm infants (29 to < 35 weeks GA) in their first RSV season. Model-based analyses of the Phase 2b clinical PK and efficacy data identified a projected serum $AUC_{0-\infty}$ of 13.4 day·mg/mL as the protective exposure threshold. The risk of medically attended RSV-confirmed LRTI over the course of the RSV season was significantly lower in infants with higher projected $AUC_{0-\infty}$. Infants with $AUC_{0-\infty}$ above 13.4 day·mg/mL had a statistically significant higher probability of protection based on exposure-response analysis using Cox proportional hazard regression. Although, the fixed 50-mg dose resulted in clinically efficacious exposures for 97% of infants weighing < 5 kg in the Phase 2b study, this dose was suboptimal for infants weighing \geq 5 kg in this study. Overall, 3% and 59% of the infants in groups weighing < 5 kg and \geq 5 kg, respectively, were in the lowest $AUC_{0-\infty}$ quartile (4.5 to 13.4 day·mg/mL) that was determined to be suboptimal. Additionally, a cut point analysis of the weight-normalized doses of all treated infants revealed that a 10 mg/kg dose was the corresponding clinically efficacious and protective threshold dose. Henceforth, based on these analyses, a stratified fixed dosing strategy by weight bands is proposed to ensure an adequate dose to maintain nirsevimab serum concentrations above the target area under the concentration-time curve throughout the RSV season. Based on dose optimization analysis designed to maximize the proportion of infants with clinically efficacious nirsevimab serum exposure, for infants entering their first RSV season a single fixed 50-mg IM dose is proposed for infants with body weight < 5 kg, while a single fixed 100-mg dose is proposed for infants weighing \geq 5 kg. The body weight range for the majority of children entering their second RSV season is expected to be approximately 8.5 to 15 kg at the time of dosing. Therefore, with the same rationale, a single fixed 200-mg dose of nirsevimab is proposed for subjects entering their second RSV season to achieve and maintain efficacious exposure during the entire second RSV season. There have been no reports that IgG1 kappa mAb compounds show obvious ethnic differences.

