**A Phase 2, Open-label, Uncontrolled, Single-dose Study to
Evaluate the Safety and Tolerability, Pharmacokinetics, and
Occurrence of Antidrug Antibody for Nirsevimab in
Immunocompromised Children \leq 24 Months of Age**

Sponsor Protocol Number: D5290C00008
Investigational Product: Nirsevimab (MEDI8897)

Sponsor: AstraZeneca AB, [name]

Medical Monitor: PPD
[REDACTED]
AstraZeneca, BioPharmaceuticals R&D

Contract Research Organization: IQVIA

Protocol History, Date:
Original Protocol, 27 Jan2020
Amendment 1, 24Apr2020
Amendment 2, 17Dec2020
Amendment 3, 23June2021

This document contains trade secrets and commercial information that is privileged or confidential and may not be disclosed without prior authorization from AstraZeneca.

PROTOCOL AMENDMENT SUMMARY OF CHANGES TABLE

DOCUMENT HISTORY	
Document	Date
Amendment 3 (CSP for global use)	23 June 2021
Amendment 2	17 Dec 2020
Amendment 1	24 April 2020
Original Protocol	27 Jan 2020

Descriptions of Amendments 1 and 2 are included in Section 9.

Protocol Amendment 3 (dated 23 June 2021)

The principal reason for this amendment is to revise the protocol to be globally applicable, in line with the decision to expand the study to include countries other than Japan, where the study is currently ongoing. At the time of the original protocol and Amendments 1 and 2, the study was planned to be conducted in Japan only. By expanding the study to additional countries and increasing the sample size, immunocompromised children with different underlying causes from different countries can be included in the study, supporting the safety evaluation in a diverse population. Additionally the increase in sample size aligns with the design and number of participants pre-determined for other high risk populations under study within the program.

Section(s)	Description of Change	Brief Rationale
Title Page	Study title revised to not include 'Japanese'	For global applicability.
Title Page	Name of medical monitor changed.	Assignment of new medical monitor.
Title page 1 Introduction 4.5 Investigational Product	Sponsor name changed from MedImmune to AstraZeneca	To clarify that MedImmune is a fully owned subsidiary of AstraZeneca.
Synopsis 2.2 Secondary Objectives 3.2.2 Rationale for Endpoints 4.8.4 Analysis of Pharmacokinetics	Pharmacokinetic endpoints revised to include only concentration of nirsevimab.	The sparse PK sampling in this study does not allow for accurate non-compartmental analysis.

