3.2.3 Rationale for Endpoints

Nirsevimab is being developed to provide RSV immunoprophylaxis for all infants and young children, including immunocompromised children ≤ 24 months of age. The primary endpoint for this study is safety and tolerability. The standard measures of TEAEs/TESAEs, AESIs, and NOCDs will be used for this assessment. All subjects will be followed for approximately 1 year after dosing with nirsevimab.

Serum concentrations of nirsevimab at selected time points will be evaluated as a secondary endpoint to confirm that serum concentrations are maintained at an efficacious level for at least 5 months after dosing. PK data will be summarized by descriptive statistics. PK data obtained in this study will be compared to the PK data from the Phase 2b, Phase 3, and the Phase 2/3 studies. For infants and children who require hospitalization for LRTI or any respiratory infection, an additional serum sample for measurement of nirsevimab concentration and ADA will be obtained contemporaneous with time of hospitalization.

To determine nirsevimab serum levels post dosing and to correlate with the potential development of ADA, serum concentrations will be measured up to 360 days post dose. ADA to nirsevimab will be measured at selected time points throughout the study and up to 360 days post dose.

This study will also summarize efficacy of nirsevimab in terms of incidence of RSV LRTI. RSV results in a significant burden of disease consisting of hospitalization, visits to the ER, and visits to outpatient clinics. This endpoint is designed to allow the capture of this total burden of disease. A separate endpoint of RSV hospitalization will also be evaluated.

Exploratory endpoints will examine CCI [REDACTED]

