4.8.4 Analysis of Pharmacokinetics

Serum concentrations of nirsevimab at selected time points will be evaluated to confirm that adequate exposures for protection from RSV LRTI are maintained for at least 5 months after dosing. Nirsevimab serum concentration data will be presented in descriptive statistics.

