## **3.2 Secondary variables**

### **3.2.1 Pharmacokinetic (PK) variables**

The PK variable is nirsevimab serum concentration.

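### Do the two Phase 2b AUC figures in Protocol 1.4.3 and 3.2.1, which cannot be one metric, require a change to the plan?

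*Protocol*

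**What the plan says.** Protocol 1.4.3 gives, for the Phase 2b study after a fixed 50-mg intramuscular dose, a mean AUC0-∞ of 5,176.3 day·µg/mL with a CV of 35.0%.

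Protocol 3.2.1 describes model-based analyses of the same study. It names a projected AUC0-∞ of "13.4 day·mg/mL as the protective exposure threshold", and places the lowest quartile at 4.5 to 13.4 day·mg/mL, which it calls suboptimal. The sentence that opens "Overall, 3% and 59% of the infants in groups weighing" gives the shares in that quartile below 5 kg and at or above 5 kg. The section uses the word projected twice and omits it twice, including where it gives the quartile.

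Protocol 1.5 links exposure to efficacy. The effect of immune "status on exposure will be evaluated using population PK methods", and "exposure matching principles will be used to support extrapolation" of efficacy from the Phase 2b and Phase 3 studies in healthy infants. It names no exposure metric and no reference value.

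On this trial's own PK data, Protocol 3.2.3 sets out "to confirm that serum concentrations are maintained at an efficacious level for at least 5 months after dosing", and Protocol 4.8.4 sets out "to confirm that adequate exposures for protection from RSV LRTI are maintained for at least 5 months after dosing". The Amendment 3 summary explains why the endpoint was reduced to concentrations: "The sparse PK sampling in this study does not allow for accurate non-compartmental analysis". SAP 3.2.1 follows: "The PK variable is nirsevimab serum concentration". SAP 4.2.5.1 is descriptive, and SAP Section 4 plans no formal comparisons.

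**The concern.** The two sections use the same symbol for the same study and dose, and the mean in one lies far below the first quartile in the other. A mean cannot sit there unless the lower tail is long, and Section 3.2.1 rules that out by putting the bottom of the lowest quartile at 4.5.

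This would matter because the trial is single-arm and its efficacy data are only summarised. The efficacy argument therefore depends on showing that exposure here matches exposure in healthy infants. The 13.4 value is the only clinical exposure threshold in the visible text. If an analyst compared AUCs from this trial with 13.4 on one scale and with the Phase 2b mean on the other, the two comparisons could point in opposite directions.

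A second worry follows. The text promises to confirm adequate exposure for five months but gives no level that would count as confirmation.

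**Working it through.** **Inputs.** Mean 5,176.3 day·µg/mL and CV 35.0% (Protocol 1.4.3). Lowest quartile 4.5 to 13.4 day·mg/mL, with 3% of infants below 5 kg and 59% of those at or above 5 kg falling in it (Protocol 3.2.1). Day 151: 97.8% of measurable concentrations above 6.8 µg/mL (Protocol 1.4.3).

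**1. Common units.** 5,176.3 / 1,000 = 5.18 day·mg/mL. SD = 0.35 × 5.1763 = 1.81.

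**2. Is Section 3.2.1 coherent on its own?** Let w be the share weighing at least 5 kg. A quartile requires 0.03(1 − w) + 0.59w = 0.25, so w = 0.22 / 0.56 = 39%. This is a possible share, so the section does not contradict itself.

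**3. Lowest mean that Section 3.2.1 allows.** A quarter of infants are at 4.5 or more and three quarters at 13.4 or more: 0.25 × 4.5 + 0.75 × 13.4 = 1.125 + 10.05 = 11.175 day·mg/mL. The ratio to the reported mean is 11.175 / 5.1763 = 2.16.

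**4. What Section 1.4.3 allows.** The value 13.4 lies (13.4 − 5.1763) / 1.812 = 4.54 SD above the mean. By Cantelli's inequality the share above it is at most 1 / (1 + 4.54²) = 4.6% under any distribution (0.15% if lognormal). Section 3.2.1 implies 75%. The highest possible first quartile is 5.1763 + 1.812 × √(1/0.75 − 1) = 6.2, against 13.4 stated.

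**5. Simple explanations.** A unit slip would be a factor of 1,000, not a factor of two to three. If Section 1.4.3 covered only infants of at least 5 kg, the mean would still have to reach 0.59 × 4.5 + 0.41 × 13.4 = 8.15. Neither removes the gap. A different derivation remains: Section 3.2.1 calls its AUC projected and model-based, and Section 1.4.3 attaches no such label to its own.

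**6. Does either AUC enter an analysis here?** In the visible text, no. The endpoint tables, Protocol 4.8.4, SAP 3.2.1 and SAP 4.2.5.1 use concentrations by visit, by dose group, by inclusion condition and by ADA status. No AUC is tabulated and none is compared with 13.4.

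**7. Would a threshold row settle the wording about confirmation?** The obvious candidate is the percentage of Day 151 values above 6.8 µg/mL. In Phase 2b, 97.8% of measurable values passed that level while 25% of infants were in the AUC quartile called suboptimal. If the denominators match (an assumption), at least 97.8 + 25 − 100 = 22.8% pass one yardstick and fail the other. The row would therefore not show that exposure is efficacious in the sense of Section 3.2.1.

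**The case for a change.** The strongest case for a change is that exposure matching is the only route from this trial to an efficacy claim. On that view its metric and reference should be fixed in writing before the data are seen. Redaction does not explain the conflict, because both AUC figures are in open text. If the explanation is two metrics, the protocol never defines the difference and drops its own label halfway through Section 3.2.1. One sentence would cost almost nothing.

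Much of this stands as a comment on drafting. A reader cannot tell from the protocol how the two AUCs differ, and the labelling in Section 3.2.1 is incomplete.

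The step from there to a defect in the plan does not stand. The reference is partly given: Section 1.5 names healthy infants in Phase 2b and Phase 3 as the comparison and population PK as the method, and Section 3.2.3 adds comparison with PK data from the Phase 2/3 study. Matching to a named reference population does not in itself need a cut-off. Since sampling here is too sparse for accurate non-compartmental analysis, any AUC would have to come from a model and be set against reference values derived the same way. A pharmacometrician would do that as a matter of course. Placing 13.4 on the Section 1.4.3 scale is a misuse that nobody proposes.

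**Conclusion.** The arithmetic is firm: read as one metric, the figures differ by a factor of at least 2.16, whatever the distribution, taking the stated mean, CV and quartile limits at face value. What it shows is an unexplained derivation in background text about an earlier study. It does not show which figure is wrong, or that either is.

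No change follows. Safety is the primary endpoint, PK is reported as concentrations with descriptive statistics, and no visible planned output would differ if the two AUCs were labelled more fully. Those doing the modelling can be expected to fill the gap by deriving exposure in the same way for this trial and its reference studies. A row for 6.8 µg/mL brings no gain: it is a nonclinical target, less demanding than the AUC threshold, and could be over-read as confirmation.

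Two limits apply. Text is blacked out after the sample-size paragraphs, in Protocol 4.8.7, and in SAP 3.3 and 4.2.6, where the amendment history records added PK and ADA analyses. A separate population PK plan may also exist. The metric and reference may be stated in any of these, so their absence from the visible text cannot be counted against the plan. The conclusion also assumes that no hidden output applies 13.4 to AUCs on the Section 1.4.3 scale. It says nothing about which dose is right.
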